#### **10.2.2 Stopping Criteria**

### 10.2.2.1 General Stopping Criteria

The study will be discontinued if any unacceptable safety findings are identified. This decision will be made jointly by the PI (or deputy) and the Sponsor. A written document signed by the PI (or deputy) and Sponsor will be produced ratifying the decision.

Individual subjects may also be withdrawn for any of the reasons outlined in Section 10.5.5.

### 10.2.2.2 Dose Stopping Criteria Within a Cohort (Part A, Part B and Part C)

Dosing of subjects in the ongoing cohort will be temporarily stopped pending evaluation of all available data if any of the following criteria are fulfilled:

• A serious adverse reaction (*i.e.* a SAE considered at least possibly related to the IMP administration) occurs in one subject.

Or

• Severe non-serious adverse reactions (*i.e.* severe non-serious AE considered at least possibly related to the IMP administration) occur in two subjects in the same cohort, independent of within or not within the same system organ class.

Or

- If two or more subjects in the dose group experience any of the following:
  - ALT or AST >3xULN, considered clinically significant and IMP related.
  - Serum Cys C increase > 25%, confirmed after repeat assessment 24-48h apart, and considered IMP related
  - o Ratio of microalbuminuria/creatininuria > 300 mg/g and considered IMP related
  - o an increase in QTcF value of >60 msec from baseline (average of baseline triplicate values) or an absolute QTcF >500 msec, both confirmed by repeat measurement after 20 minutes in resting position, and considered IMP related.

#### 10.2.2.3 Dose Escalation Stopping Criteria

Dose escalation between cohorts in Part A (and between Part A and Part B) will be temporarily stopped pending evaluation of all available data if any of the following criteria are fulfilled:

• A serious adverse reaction (*i.e.* a SAE considered at least possibly related to the IMP administration) occurs in one subject.

Or

• Severe non-serious adverse reactions (*i.e.*, severe non-serious AE considered as, at least possibly related to the IMP administration) occur in two subjects in the same cohort, independent of within or not within the same system organ class.

Or

• If two or more subjects in the preceding dose group experience any of the following:

DNDi RD 777/34920 DNDi- 0690- 02

Final V3.0/ Date 07 December 2020

Confidential

Page 50 of 109

- o ALT or AST >3xULN, considered clinically significant and IMP related.
- Serum Cys C increase > 25%, confirmed after repeat assessment 24-48h apart, and considered IMP related.
- o Ratio of microalbuminuria/creatininuria >300 mg/g and considered IMP related.
- o an increase in QTcF value of >60 msec from baseline (average of baseline triplicate values) or an absolute QTcF >500 msec, both confirmed by repeat measurement after 20 minutes in resting position, and considered IMP related.

Or

- If one or more subjects in the preceding dose group experience:
  - o an increase in troponin I concentration which is considered clinically significant by the Investigator (with reference to the change from baseline value) and considered IMP related.

Or

• If the dose in a single subject is anticipated to exceed an AUC0-tau of  $\geq 100 \, \mu g^*h/mL$ . These limits are based on the exposure observed at the 20 mg/kg in cynomolgus monkeys (NOAEL: AUC0-24 of 101  $\mu g^*h/mL$  in male and 111  $\mu g^*h/mL$  in females).

Or

• If the dose in a single subject is anticipated to exceed a  $C_{max}$  of  $\geq 8.0 \ \mu g/mL$ . These limits are based on the exposure observed at the 20 mg/kg in cynomolgus monkeys (NOAEL:  $C_{max}$  of  $8.03 \ \mu g/mL$  in males and  $9.03 \ \mu g/mL$  in females).

Dose escalation between cohorts in Part A will be limited to a maximal 3-fold increase, and 2-fold increase between Part A and Part B, depending on safety and tolerability data and predicted exposure (both AUC and  $C_{max}$ ).

If any of the above criteria are fulfilled, the cases will be discussed at the SRC who could proceed with partial or full unblinding as necessary to take its decision to either dose-escalate, proceed to enlargement of the cohort, or explore a lower dose.

If any of the stopping criteria occurred in a subject receiving DNDI-0690 the trial will put on halt and further dosing can be resumed only once an appropriate substantial amendment has been submitted and received regulatory and ethical approval from the relevant ethics committee and competent authority.

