### Part A: Multiple Ascending Dose Cohorts (Cohorts 1-4)

Part A will consist of up to 4 cohorts of 9 subjects. Subjects will be randomly assigned to receive an oral dose of active IMP (6 subjects) or matching placebo (3 subjects) for 10 days in a sequential escalating manner with a minimum of 7 days interval between two cohorts.

In Part A, each cohort will follow a sentinel dose-escalation schedule; two (2) subjects will be dosed on the first dosing day of each cohort (1 subject on active IMP and 1 subject on matching placebo). The remainder of the cohort (5 subjects on active IMP and 2 subjects on matching placebo) will be dosed a minimum of 48 hours later pending confirmation of an acceptable safety profile in the dose-leader cohort by the Principal Investigator (PI), or medically-qualified designees who are familiar with the study protocol and Investigator's Brochure (IB).

The planned starting dose for Cohort 1 is 400 mg of DNDI-0690 once a day for 10 days. Doses to be administered in Cohorts 2 to 4 will be determined based on emerging PK and safety data. The number of daily doses may be increased to 2 by implementation of a twice a day (BID) dosing regimen if the number of capsules in a single intake is raising concerns of acceptability. This decision will be made by the Safety Review Committee (SRC) prior to each cohort and will apply to all subjects within a cohort.

Dose escalation between cohorts in Part A (and between Part A and Part B) will be temporarily stopped pending evaluation of all available data if any of the following criteria are fulfilled:

• A serious adverse reaction (*i.e.* a serious adverse event (SAE) considered at least possibly related to the IMP administration) occurs in one subject.

Or

• Severe non-serious adverse reactions (*i.e.* severe non-serious AE considered as, at least possibly related to the IMP administration) occur in two subjects in the same cohort, independent of within or not within the same system organ class.

Or

- If two or more subjects in the preceding dose group experience any of the following:
  - Alanine aminotransferase (ALT) or aspartate aminotransferase (AST) >3x upper limit of normal (ULN), considered clinically significant and IMP related.
  - Serum Cystatin C (Cys C) increase > 25%, confirmed after repeat assessment 24-48h apart, and considered IMP related.
  - o Ratio of microalbuminuria/creatininuria >300 mg/g and considered IMP related.

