  - An increase in corrected QT interval by Fridericia's formula (QTcF) value of >60 msec from baseline (average of baseline triplicate values) or an absolute QTcF >500 msec, both confirmed by repeat measurement after 20 minutes in resting position, and considered IMP related.

Or

- If one or more subjects in the preceding dose group experience:
  - o An increase in troponin I concentration which is considered clinically significant by the Investigator (with reference to the change from baseline value) and considered IMP related.

Or

• If the dose in a single subject is anticipated to exceed an AUC from time of dosing to the end of the dosing interval (AUC0-tau) of  $\geq$ 100 µg\*h/mL. These limits are based on the exposure observed at the 20 mg/kg in cynomolgus monkeys (no observed adverse effect level (NOAEL): AUC0-24 of 101 µg\*h/mL in male and 111 µg\*h/mL in females).

DNDi RD 777/34920 DNDi- 0690- 02

Final V3.0/ Date 07 December 2020

Confidential

Page 9 of 109

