#### Or

• If the dose in a single subject is anticipated to exceed a maximum concentration ( $C_{max}$ ) of  $\geq 8.0 \ \mu g/mL$ . These limits are based on the exposure observed at the 20 mg/kg in cynomolgus monkeys (NOAEL:  $C_{max}$  of  $8.03 \ \mu g/mL$  in males and  $9.03 \ \mu g/mL$  in females).

Dose escalation between cohorts in Part A will be limited to a maximal 3-fold increase, and 2-fold increase between Part A and Part B, depending on safety and tolerability data and predicted exposure (both AUC and  $C_{max}$ ).

If any of the above criteria are fulfilled, the cases will be discussed at the SRC who could proceed with partial or full unblinding as necessary to take its decision to either dose-escalate, proceed to enlargement of the cohort, or explore a lower dose.

If any of the stopping criteria occurred in a subject receiving DNDI-0690 the trial will put on halt and further dosing can be resumed only once an appropriate substantial amendment has been submitted and received regulatory and ethical approval from the relevant ethics committee and competent authority.

Each cohort will follow the same study design including Screening Period, Treatment Period and Post Study Follow-up. The study sequence for Part A is presented in Figure 1.

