#### Day 10:

On Day 10, only a morning dose will be administered.

- Start Holter monitoring (for extraction of ECGs) at approximately 60 minutes prior to dosing (Holter will be on for at least 25 hours and can only be removed after 24 h post-last dose PK blood samples are collected)
- Eligibility check: Pre-dose
- O Dosing (morning only on Day 10, even if BID regimen implemented)
- Laboratory safety tests (biochemistry, haematology, coagulation, urinalysis, urine microscopy): Pre-dose
- o Troponin I: Pre-dose
- o 12-lead ECG: Pre-dose and 4 h post-dose
- Vital signs (supine systolic and diastolic blood pressure, pulse rate and tympanic temperature):
   Pre-dose
- o AE
- o SAE
- Prior and concomitant medication
- PK plasma sample for DNDI-0690 and metabolite: Pre-dose and 0.5, 1, 2, 3, 3.5, 4, 6, 9, 12 h post-dose
- O DBS samples for DNDI-0690: Pre-dose and 0.5, 1, 2, 3, 3.5, 4, 6, 9, 12 h post-dose
- o PK urine samples for DNDI-0690:[0-24] h post-dose
- Urine samples for exploratory biomarkers: Pre-dose
- Full blood sampling for transcriptional profiling (mRNA) assessment (**Only performed on Cohort 2 and Cohort 3**)

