A Pathology Working Group (PWG) was constituted to review the data on testes. For the 7–day study, the PWG concluded that the testicular effect of vacuolation was a background change and that the effects seen were all considered as fixation artefact and thus the testicular histology was all concluded to be within the normal. In the case of the 28-day study, the PWG confirmed following review the presence of changes in the testes of animals at the two highest doses of 100 and 400 mg/kg/day (the same animals as in the initial report) where the finding was described by the PWG as segmental tubular dilation with associated thinning/atrophy of the seminiferous epithelium. This distribution could suggest a potential relationship to treatment. However, based upon the segmental nature of the finding, the frequent unilateral distribution and the fact that this finding has been described in a number of publications as a background change in young cynomolgus monkeys, it was concluded that the findings in the testes were a background lesion and unrelated to treatment. In conclusion, treatment with DNDI-0690 for 7 or 28 days is not considered to induce any testicular changes or toxicity.

Confidential

Final V3.0/ Date 07 December 2020

Page 40 of 109

Table 3 Summary of Toxicokinetic and Pharmacokinetic Parameters for DNDI-0690\*

Species / Day	Gender	Type of study	Dose PO (mg/kg/day)	C max (µg/mL)	AUC 0-24 (μg.h/mL)
Rat /	M	Toxicology TK	1000 (500 bid) NOAEL 28 days	$11.3 \pm 0.693$	180 ± 22.5
Day 28	F	Toxicology TK	1000 (500 bid) NOAEL 28 days	16.9 ± 1.47	307 ± 36.8
Monkey /	M Toxicology TK		20 (10 bid) NOAEL 28 days	$8.03 \pm 0.367$	101 ± 7.85
Day 28	F	Toxicology TK	20 (10 bid) NOAEL 28 days	$9.03 \pm 6.78$	111 ± 61.2

\* methodology, additional doses and time-points available in the IB

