### 8.7 Risk/Benefit Assessment

No benefit will be observed in healthy volunteers.

The risk/benefit ratio of the proposed study is considered acceptable. Several measures to minimize the risks to healthy subjects have been taken with respect to the following study design elements:

- For each cohort in Part A and Part B, 2 subjects (1 subject on active drug and a subject on matching placebo) will be dosed and monitored for 48 hours prior to dosing the rest of the cohort.
- Dose escalation (during Part A and between Part A and Part B) will be done in a stepwise, controlled manner, with dose escalation only being permitted after full evaluation of the available safety data from the previous cohort by the SRC.
- Clinical laboratory monitoring: At time of study entry, study participants are required to have safety laboratory values within acceptable ranges. Serial measurements of safety laboratory parameters (Biochemistry and haematology which include platelet count, renal/liver function tests, renal integrity monitoring) and coagulation parameters are planned with interim reviews as defined in the SRC charter.
- Close cardiac safety monitoring by regular ECG assessments.
- Study eligibility: The healthy subject/patient inclusion and exclusion criteria have been incorporated to minimize any risk of an exaggerated pharmacological effect of DNDI-0690.
- The evaluation of GFR by a reference method in Part C will be performed at the end of the trial. The dose level used in Part C will be tested in Part A and will have no impact on the safety of the volunteers.
- The starting dose in Part A of this study is 400 mg once daily for 10 days which is considered to be safe and is well below the highest dose level of 3600 mg DNDI-0690 administered in the SAD study. It is expected that the maximum values of  $C_{max}$  and  $AUC_{0-24}$  in individual subjects in Part A Cohort 1 will be well below the PK stopping criteria of  $C_{max} \ge 8000$  ng/mL or  $AUC_{0-24} \ge 100,000$  ng,h/mL.

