  - Ae%: % of dose excreted in urine over each collection interval (0 to 24 h post-dose).
  - CLR: Renal clearance

If BID dosing, AUC0-10, AUC0-10/D, AUC0-10h,norm will be added on Day 1 and Day10.

Derived PK parameters will be listed along with the points used to calculate  $k_{el}$  (lower, upper and number used) and  $R^2$  adjusted. The derived PK parameters will also be summarised. The descriptive statistics presented will be N, n, arithmetic mean, geometric mean (with the exception of  $T_{max}$ ), SD, coefficient of variation (CV%), minimum, median and maximum.

**Dose Proportionality/Independence (Part A and Part B):** For Day 1 and Day 10 (Part A) OR Day 1 and Day 5 (Part B), dose proportionality will be assessed by performing a regression analysis of the log-transformed  $C_{max}$ ,  $AUC_{0-\tau}$  and  $AUC_{0-inf}$  (Day 10 for Part A and Day 5 for Part B only) values versus the log-transformed dose using the power model with a fixed effect for log(dose). For each parameter a point estimate and 95 % confidence interval (CI) will be calculated for the slope of the regression line.

For Day 10 for Part A and Day 5 for Part B, dose independence will be assessed for t½ and CL/F by performing a regression analysis of the untransformed parameters versus dose with a fixed effect for dose. For each parameter a point estimate and corresponding 95 % CI will be calculated for the slope of the regression line.

**Steady-State** (**Part A and Part B**): For each dose level, log-transformed trough concentration levels at pre-dose each day (Day 2 to Day 10 for Part A and Day 2 to Day 5 for Part B) will be subjected to a mixed effects analysis of variance (ANOVA) with study day as a fixed effect and subject as a random effect in order to establish whether and when steady-state has been attained for each dose level. Back-transformed ratios for the comparisons of each consecutive day (*i.e.* Day 3/Day 2) will be presented along with corresponding 90 % CI.

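### The AUC stopping limit is a full-day monkey exposure applied per dosing interval, so in a twice-daily Part A cohort it cannot trigger before the Cmax limit

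*Protocol*

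**What the plan says.** Section 10.2.2.3 and the Synopsis hold escalation if a single subject's anticipated AUC0-tau reaches 100 µg·h/mL: "If the dose in a single subject is anticipated to exceed an AUC 0-tau of" that value. The Synopsis spells the metric out: "exceed an AUC from time of dosing to the end of the dosing interval". A parallel rule applies at 8.0 µg/mL: "If the dose in a single subject is anticipated to exceed a maximum concentration".

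The same bullet gives the source of the AUC number: the monkey NOAEL AUC0-24, 101 µg·h/mL in males and 111 in females. Table 3 (Section 8.5.1) lists that dose level as "20 (10 bid) NOAEL 28 days", so each figure is a 24-hour exposure from two doses.

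Section 8.7 says Cohort 1 exposures "will be well below the PK stopping criteria of" Cmax 8000 ng/mL or AUC0-24 100,000 ng·h/mL. There the metric is AUC0-24.

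Twice-daily dosing is allowed in Part A: "The number of daily doses may be increased to 2 by implementation of a twice a day (BID) dosing regimen". Table 1 lists it as an option for Cohorts 2 to 4. Section 10.5.3.1 puts the second dose 10 h after the first, and Section 10.9.2.5.4 adds the matching interval parameter: "If BID dosing, AUC 0-10 , AUC 0-10 /D". On the last day the evening dose is dropped: "Dosing (morning only on Day 10, even if BID regimen implemented". Section 10.2.1 gives the escalation review Cmax and AUC0-24 from the 24 h after the last dose.

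**The concern.** The threshold is a daily quantity and the operative rule applies it to one dosing interval. With once-daily dosing that makes no difference. With twice-daily dosing the interval holds well under half of the day's exposure, yet the number stays at 100.

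The AUC rule is also most needed under twice-daily dosing. Splitting the dose lowers the peak for a given daily AUC, so the Cmax rule acts later than it would once daily. If the AUC rule cannot act either, a subject's anticipated daily exposure can pass the NOAEL-based figure with no exposure stop. Section 8.5.1 reports a death with severe renal and cardiac effects at the next monkey dose level, 100 mg/kg/day, so this is the margin the rule is meant to protect.

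**Working it through.** **Plan's own figures.** Section 8.6.1 puts the highest individual single-dose exposures at 3600 mg (Cmax 3160 ng/mL, AUC0-24 42,600 ng·h/mL) 60.5% and 57.4% below the cap. 1 − 3160/8000 = 60.5% and 1 − 42,600/100,000 = 57.4%. Both reproduce, with the cap on AUC0-24.

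**Bound that needs no model.** Over an interval of length τ, AUC0-τ ≤ Cmax × τ. With Cmax below 8.0 µg/mL:

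| τ (h) | AUC0-τ is below |
|---|---|
| 10 | 80 |
| 12 | 96 |
| 14 | 112 |
| 24 | 192 |

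Reaching AUC0-10 = 100 takes a mean concentration of 100/10 = 10 µg/mL, already above the Cmax limit.

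**Once-daily comparison (Table 4, predicted steady state).** AUC/Cmax is 13.1/1.24 = 10.6 h at 400 mg, 23.6/1.99 = 11.9 h at 1200 mg and 44.9/3.38 = 13.3 h at 3600 mg. Multiplied by 8 µg/mL, the Cmax limit corresponds to a daily AUC of 85, 95 and 106. Once daily, the two limits bind at about the same exposure.

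**Twice-daily shape.** One-compartment oral model at steady state, doses at 0 and 10 h of each 24 h. Half-lives are the ends of the range in Section 8.6.1. The absorption rate ka is my assumption (0.8/h), because the protocol gives none.

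| Quantity | t½ 4.547 h | t½ 12.144 h |
|---|---|---|
| AUC0-10 as share of daily AUC | 0.437 | 0.417 |
| Cmax when daily AUC = 100 (µg/mL) | 6.80 | 5.18 |
| One-dose Day 10 AUC0-24 as share of daily AUC | 0.573 | 0.742 |
| Daily AUC when Cmax = 8 | 118 | 155 |
| Same, if only the Day 10 morning peak is seen | 131 | 168 |
| AUC0-10 when Cmax = 8 | 51 | 64 |

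At a true daily AUC of 100 the review would see an AUC0-10 of 42–44, a Cmax of 5.2–6.8 µg/mL and a Day 10 AUC0-24 of 57–74. None reaches a limit. For ka from 0.4 to 2.0/h, the Cmax limit acts at a daily AUC of 102–164 (112–179 on the morning peak alone).

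**How likely this is at the Part A ceiling.** Section 10.3.1 caps Part A at 2400 mg/day, for example 1200 mg twice daily. Doubling the 1200 mg row of Table 4 gives a geometric mean daily AUC of 2 × 23.6 = 47.2 µg·h/mL (males). Assuming a lognormal distribution, σ = √ln(1 + CV²) and p = P(Z > ln(100/47.2)/σ), with 6 active subjects:

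| CV used | σ | z | p | At least 1 of 6: 1 − (1 − p)⁶ |
|---|---|---|---|---|
| 23.5% (3600 mg row) | 0.232 | 3.24 | 0.0006 | 0.4% |
| 64.2% (1200 mg row) | 0.587 | 1.28 | 0.101 | 47% |

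**The case against.** A sensible reviewer could read the limit as daily. Its basis in the same bullet is AUC0-24, Section 8.7 says AUC0-24, and Table 4 labels its once-daily 24-hour prediction AUC(0-tau), which may be where the wording came from. No text sets tau to 10 h for the stopping rule. With unequal intervals, the 14 h overnight interval allows up to 112 below the Cmax limit, so 100 is arithmetically reachable. The trigger is a prediction, and Section 10.2.2.3 separately ties each escalation step to predicted AUC and Cmax. Renal, hepatic, troponin and QTcF stops remain. Twice-daily dosing may never be used: 2400 mg is 12 capsules of 200 mg, and 18 were given at once in the single-dose study.

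The daily reading is the right intention, but it contradicts the defined metric, and a stopping rule should not depend on which section is consulted. The 14 h interval qualifies the strict bound without rescuing the rule: in the same model over the wider ka range, the overnight AUC is at most about 96 when Cmax reaches 8. Reading the reviewed AUC0-24 instead does not help, because on Day 10 it holds one dose. Day 1 AUC0-24 does hold both, but it is not at steady state and is sparsely sampled after the evening dose. The other stops respond to observed harm, whereas this one is meant to act beforehand.

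Two points stand. The scope is conditional on twice-daily dosing. The probability range is wide and turns on which Table 4 CV applies; it shows only that the situation cannot be ruled out.

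**Conclusion.** The concern holds and should be fixed. The safety threshold is written in a metric that matches neither its source nor Section 8.7. For the 10 h interval the protocol sets and derives, it is a strict arithmetic result that the AUC rule cannot trigger before the Cmax rule. How far daily AUC can pass 100 before Cmax stops escalation depends on the model: to about 118–155 at ka 0.8/h, and 102–164 across ka 0.4–2.0/h, assuming one compartment and linear superposition. Section 8.6.1 describes decline that is sometimes biphasic, so these figures are indicative. The defect affects only a Part A cohort dosed twice daily. Cohort 1, Part B and Part C are once daily, where the two metrics coincide.

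**What to change.** In Section 10.2.2.3 and the Synopsis, restate the limit as an anticipated steady-state AUC0-24 of 100 µg·h/mL or more, defined as total daily exposure including both doses under twice-daily dosing. This agrees with Section 8.7 and the monkey basis.

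In Section 10.2.1, require the PK summary for any twice-daily cohort to report that two-dose 24-hour exposure. The omitted Day 10 evening dose can be added by superposition, the method already used for Table 4. Label the result separately from the one-dose Day 10 AUC0-24, which would otherwise be compared with the limit and understate exposure.

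The cost is one wording change in two places and one derived quantity, with no new samples and no effect on once-daily cohorts. Because it alters a stopping criterion, it will probably need a substantial amendment.

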### Twice daily dosing (BID) regimen if needed:

- If a BID regimen is implemented, subjects will fast overnight for at least 10 hours (h) before each morning dose.
- The second, evening dose will be administered 10 hours following the morning dose. The second, evening dose shall be taken a minimum of 5 hours post mid-day meal, and one hour before the dinner.
- On Day 10, only a morning dose will be administered.
- Lunch will be served: approximately 4 h post-morning dose.
- Receive second, evening dose of the day: 10 h post-morningdose
- Dinner will be served: approximately 12 h post-morningdose.

On all non-dosing study days, whilst resident in the clinical unit, meals will be served at standard times. Subjects will choose meals from a standard menu while resident at the clinical unit.

Subjects are required to fast for at least 8 h or 10 h prior to laboratory sample collection for the following tests:

• For blood glucose tests (analysed in serum), require at least 8 h fasting period for fasted glucose test.

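### Under the optional BID regimen the AUC0-tau escalation limit covers only one of two daily doses, although its value of 100 µg·h/mL comes from a 24-hour monkey AUC

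*Protocol*

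**What the plan says.** The synopsis (section 3, Part A) and section 10.2.2.3 list the AUC criterion among the reasons to stop dose escalation. Section 10.2.2.3 opens it with "If the dose in a single subject is anticipated to exceed" and names AUC0-tau. The synopsis wording is: "If the dose in a single subject is anticipated to exceed an AUC from time of dosing to the end of the dosing interval", with a limit of 100 µg·h/mL. Both places give the source of the number: the monkey no-observed-adverse-effect dose of 20 mg/kg, with AUC0-24 of 101 µg·h/mL in males and 111 in females. Section 8.5.1 and Table 3 show that this dose was given as 10 mg/kg twice a day, so the monkey AUC0-24 covers two doses.

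The abbreviations list defines AUC0-tau over the dosing interval, as the synopsis does. Section 8.7 gives the same limit as an AUC0-24, saying that values "in individual subjects in Part A Cohort 1 will be well below the PK stopping criteria of" Cmax 8000 ng/mL or AUC0-24 100,000 ng·h/mL.

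Cohort 1 is fixed at 400 mg once daily. For later Part A cohorts the synopsis adds: "The number of daily doses may be increased to 2 by implementation of a twice a day (BID) dosing regimen". Table 1 repeats the option for Cohorts 2 to 4. Section 10.5.3.1 sets the timing: "The second, evening dose will be administered 10 hours following the morning dose". The secondary endpoints accordingly add AUC0-10 if BID is used. The Day 10 schedule states: "On Day 10, only a morning dose will be administered". Section 10.2.1 requires at least Cmax and AUC0-24, from data up to 24 h after the last dose, for each escalation decision.

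**The concern.** A limit on exposure protects subjects only if the measured quantity matches the one from which the limit was derived. Here the reference is a full day of exposure from two doses. Under human BID dosing the quantity named in the rule is exposure from a single interval. Applied literally, the cap would allow about twice the daily exposure it was meant to allow.

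The cap matters because, in the 4-week monkey study (section 8.5.1), renal toxicity and the death of one female occurred at 100 mg/kg/day, the next dose tested above the no-effect dose, and another female died at 400 mg/kg/day. The AUC cap is the rule meant to keep human exposure at or below the no-effect level, and it should hold under every regimen the protocol permits.

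**Working it through.** **Inputs.** Cap 100 µg·h/mL (section 10.2.2.3); monkey AUC0-24 of 101 and 111 (Table 3); human half-life 4.547 to 12.144 h (section 8.6.1); BID doses at 0 and 10 h (section 10.5.3.1); predicted once-daily steady-state AUC0-tau in males (Table 4). Assumptions not in the protocol: one-compartment kinetics, absorption rate constant 0.5 to 3 per hour, equal absorption morning and evening.

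**1. Units and the plan's own figures.** 100 µg·h/mL = 100,000 ng·h/mL, so sections 8.7 and 10.2.2.3 use the same number. Section 8.6.1 puts the highest single-dose values 60.5% and 57.4% below the caps: 1 − 3160/8000 = 0.605 and 1 − 42,600/100,000 = 0.574. Both reproduce.

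**2. Once daily.** The interval is 24 h, so AUC0-tau = AUC0-24 and there is no discrepancy.

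**3. BID: share of the daily AUC in each interval.** Let F(t) be the fraction of one dose's total AUC accrued by time t after dosing:

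F(t) = 1 − [ka·exp(−kt) − k·exp(−ka·t)]/(ka − k), with k = ln 2/half-life.

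At steady state the daily AUC is 2 in units of one dose's total AUC. The AUC from 0 to 10 h is the sum over n = 0, 1, 2, … of [F(24n+10) − F(24n)] + [F(24n+24) − F(24n+14)].

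- 10 h interval: 41.3% to 44.6% of the daily AUC. An interval AUC of 100 then means a daily AUC of 100/0.446 = 224 to 100/0.413 = 242.
- 14 h interval (evening to next morning): 55.4% to 58.7%. An interval AUC of 100 then means a daily AUC of 100/0.587 = 170 to 100/0.554 = 181.

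Whichever interval is taken as tau, the literal limit corresponds to a daily AUC of about 170 to 240, or 1.7 to 2.4 times the cap.

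**4. Does the Day 10 AUC0-24 help?** With the Day 10 evening dose omitted, AUC0-24 is [2 − F(14)]/2 of a full BID day. This gives 56% (half-life 4.547 h, fast absorption) to 75% (12.144 h, slow absorption). It also understates daily exposure.

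**5. How likely is it to matter?** Use a log-normal distribution with sigma = sqrt(ln(1 + CV²)), p = 1 − Φ(ln(100/GM)/sigma), and chance for at least one of 6 active subjects = 1 − (1 − p)^6.

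- Once daily, from Table 4: 400 mg (GM 13.1, CV 65.8%) 0.2%; 1200 mg (23.6, 64.2%) 4.1%; 3600 mg (44.9, 23.5%) 0.2%.
- Example of 1200 mg BID, which is 2400 mg/day, the highest scheduled Part A dose (section 10.3.1). Daily GM = 2 × 23.6 = 47.2. The chance that at least one of 6 has a daily AUC of 100 or more is 0.4%, 22% or 47% for a CV of 23.5%, 45% or 64.2%; 45% is an assumed middle value.
- Same example, interval AUC of 100 or more at CV 64.2%. For the 10 h interval, GM = 47.2 × 0.413 to 47.2 × 0.446 = 19.5 to 21.1, giving 1.6% to 2.4%. For the 14 h interval, GM = 47.2 × 0.554 to 47.2 × 0.587 = 26.1 to 27.7, giving 6.5% to 8.4%.

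At the higher CV the literal rule would therefore miss most of the cases that a 24 h limit would catch.

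**The case against.** BID is contingent. It is open only to Part A Cohorts 2 to 4, and only if the number of capsules in one intake becomes a concern. Parts B and C are once daily. In the single-dose study 3600 mg was given as 18 capsules in one intake and was well tolerated, and 2400 mg is only 12 capsules of 200 mg. Section 8.7 already uses AUC0-24, and section 10.2.1 requires AUC0-24 whatever the regimen. This limits the weight of the point but does not remove it. The operative rule names AUC0-tau. Section 8.7 speaks of once-daily Cohort 1, where the labels coincide. The AUC0-24 available under BID lacks the evening dose.

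A reader might infer something stronger: that because the rule speaks of an anticipated exposure, a measured value above the limit would not stop anything, or that section 8.7 contradicts section 10.2.2.3. The documents do not support this. A rule for the next dose can only use predicted exposure. Observed Cmax and AUC0-24 are reviewed before each escalation, and an observed exceedance makes a higher dose anticipated to exceed. Section 8.7 treats the same limits as stopping criteria for individual subjects, and section 10.2.2.3 adds: "If any of the stopping criteria occurred in a subject receiving DNDI-0690 the trial will put on halt". Read together, these already give the safe answer. That halt wording was inserted after a regulator's letter of non-acceptance (section 2) and should not be narrowed.

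A reader might also take 47% as the expected chance of exceedance. It is only the top of a 0.4% to 47% range, and it depends on carrying the 1200 mg CV over to the summed day.

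**Conclusion.** The AUC limit is wrong as written, but only for BID dosing in Part A Cohorts 2 to 4. There the literal limit is met at a daily AUC of about 170 to 240 µg·h/mL, against a reference of 101 to 111. The size rests on one-compartment kinetics and equal absorption of the two doses. The direction does not: one interval of a two-dose day holds less than the whole day's AUC. Once-daily dosing is unaffected, and exceedance is unlikely at the tabulated once-daily doses. The point is minor.

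**What to change.** In the synopsis and in section 10.2.2.3, replace AUC0-tau by total AUC over 24 h at steady state (AUC0-24), meaning the sum over both dosing intervals if BID. This matches section 8.7 and the monkey reference value.

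State also that under BID this total is predicted from the Day 10 profile by adding the omitted evening dose, for example by the superposition already used in section 10.3.1, with a conservative allowance for evening absorption. A fixed multiple of AUC0-10 should not be used. Equal absorption would suggest a multiple of 2.24 to 2.42 (1/0.446 to 1/0.413), but the evening dose is taken shortly before dinner, and section 8.6.1 reports 67% to 75% higher exposure in the fed state. If evening absorption were 1.35 to 1.7 times morning absorption (an assumption), a multiple of 2.4 would recover only about 85% to 96% of the daily AUC, which errs on the unsafe side.

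Leave the halt wording as it is. The cost is a small change to a safety rule, which may have to be handled as an amendment, and a stricter cap if BID is adopted. No new samples or visits are needed.
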